9.1.3 Serious Adverse Events

A serious adverse event is defined as an adverse event that meets at least 1 of the following serious criteria (unless it meets the definition of a Disease Related Event as defined in Section 9.1.1):

- fatal
- life threatening (places the subject at immediate risk of death)
- requires inpatient hospitalization or prolongation of existing hospitalization
- results in persistent or significant disability/incapacity
- congenital anomaly/birth defect
- other medically important serious event

A disease related event (eg, disease progression) is to be reported as a serious adverse event if:

- the subject's pre-existing condition becomes worse than what the investigator would consider typical for a patient with the same underlying condition, or
- if the investigator believes a causal relationship exists between the investigational medicinal product(s)/protocol-required therapies and the event,
- and the event meets at least 1 of the serious criteria.

An adverse event would meet the criterion of "requires hospitalization," if the event necessitated an admission to a health care facility (eg, overnight stay).

If an investigator considers an event to be clinically important, but it does not meet any of the serious criteria, the event could be classified as a serious adverse event under the criterion of "other medically important serious event." Examples of such events could include allergic bronchospasm, convulsions, blood dyscrasias, DILI (see [Appendix A](#) for DILI reporting criteria), or events that necessitate an emergency room visit, outpatient surgery, or urgent intervention. Serious adverse events, or follow-up to a serious adverse event, must be reported within 24 hours for the time period beginning with signing of informed consent through 90 days following cessation of treatment, or 30 days following cessation of treatment if the subject initiates new anticancer therapy, whichever is earlier.

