9.2.1.2 Reporting Procedures For Disease Related Events That Meet Serious Criteria

The investigator is responsible for ensuring that all serious Disease Related Events observed by the investigator or reported by the subject that occur after the first dose of investigational medicinal product(s)/study treatment/protocol-required therapies through 90 days following cessation of treatment, or 30 days following cessation of treatment if the subject initiates new anticancer therapy (whichever is earlier), are recorded on the Event CRF as a serious Disease Related Event.

All serious **Disease Related Events** will be recorded and reported to the sponsor or designee within 24 hours **of the investigator's knowledge of the event**. The investigator will submit any updated serious **Disease Related Event** data to the sponsor within 24 hours of it being available.

Disease Related Events assessed by the investigator to be more severe than expected (**unexpected worsening of disease**) or related to the investigational medicinal product(s)/study treatment/protocol-required therapies, and determined to be serious (**see Section 9.1.3**), must be recorded on the Event CRF as Serious Adverse Events and recorded and reported per Section 9.2.2.2 and Section 9.2.2.3.

Additionally, the investigator is required to report a fatal Disease Related Event on the Event CRF as a serious Disease Related Event and should be recorded and reported to the sponsor or designee within 24 hours of the investigator's knowledge of the event.

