9.2.2.2 Reporting Procedures for Serious Adverse Events

The investigator is responsible for ensuring that all serious adverse events observed by the investigator or reported by the subject that occur after signing of the ICF through 90 days following cessation of treatment, or 30 days following cessation of treatment if the subject initiates new anticancer therapy, whichever is earlier, are recorded in the subject's medical record and are submitted to Amgen. During long-term follow-up, any serious adverse event that is determined to be related to protocol-required therapy should be reported. All serious adverse events must be submitted to Amgen within 24 hours following the investigator's knowledge of the event via the Event CRF.

If the EDC system is unavailable to the site staff to report the serious adverse event, the information is to be reported to Amgen via an electronic Serious Adverse Event (eSAE) Contingency Report Form within 24 hours of the investigator's knowledge of the event. See [Appendix B](#) for a sample of the Serious Adverse Event Worksheet /eSAE Contingency Report Form.

The investigator must assess whether the serious adverse event is possibly related to the investigational product(s). This relationship is indicated by a "yes" or "no" response to the question: Is there a reasonable possibility that the event may have been caused by the investigational products. Investigational products in this study are blinatumomab and pembrolizumab.

The investigator is expected to follow reported serious adverse events until stabilization or resolution.

New information relating to a previously reported serious adverse event must be submitted to Amgen. All new information for serious adverse events must be sent to Amgen within 24 hours following knowledge of the new information. If specifically requested, the investigator may need to provide additional follow-up information, such as discharge summaries, medical records, or extracts from the medical records. Information provided about the serious adverse event must be consistent with that recorded on the Event CRF.

If a subject is permanently withdrawn from protocol-required therapies because of a serious adverse event, this information must be submitted to Amgen.

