Relative dose intensity at the target dose is the actual exposure duration at target dose divided by planned duration of target dose, which is 49 days for cohort Ia, and 42 days for cohort IIa and IIIa in cycle 1; and 21 days for cohort Ia, and 14 days for cohort IIa and IIIa in cycle 2. Subjects who didn't reach the target dose are considered having actual exposure duration as 0.

Study Day

Study Day 1 is defined as the day of first dose of blinatumomab.

And Study Day is defined as:

Pre study day 1: study day= (date – date of study day 1)

Post study day 1: study day= (date - date of study day 1) + 1

Subject Level End of Study (EOS) Date

End of Study for each subject is defined as the date the subject last completed a protocol-specified procedure. The date will be recorded on the End of Study CRF page.

Treatment Emergent Adverse Event (AE)

Treatment emergent adverse event refers to an adverse event that starts on or after first dose of blinatumomab up to and including 30 days after the end of blinatumomab or pembrolizumab whichever is later. It is indicated by a flag whether an event start before first dose of blinatumomab on the Event CRF page. This reporting window also applies to treatment-emergent serious adverse events (SAEs).

Treatment Emergent Disease-related Event (DRE)

Treatment emergent disease-related event refers to a disease-related event that starts on or after first dose of blinatumomab up to and including 30 days after the end of blinatumomab or pembrolizumab whichever is later. It is indicated by a flag whether an event start before first dose of blinatumomab on the Event CRF page.

Disease-related events assessed by the investigator to be more severe than expected and/or related to the investigational product(s)/study treatment/protocol-required therapies, and determined to be serious, must be reported on the Event CRF as serious adverse events.

Treatment Emergent Event of Clinical Interest (ECI)

ECI is defined in Section 9.1.4 of the protocol. Treatment emergent ECI refers to an ECI that starts on or after first dose of blinatumomab up to and including 30 days after the end of blinatumomab or pembrolizumab whichever is later.

Primary Completion: The primary completion date is defined as the date when the last subject is assessed or receives an intervention for the final collection of data for the primary endpoint(s), whether the study concluded as planned in the protocol or was terminated early.

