10.6.2 Adverse Events and Disease Related Events

The Medical Dictionary for Regulatory Activities (MedDRA) version 22.1 or later will be used to code all events categorized as adverse events (AEs) or disease-related events (DREs) to a system organ class and a preferred term. AEs of interest (EOI) categories will be based on search strategies defined by Medical Coding. **Treatment emergent adverse event refers to an adverse event that starts on or after first dose of blinatumomab up to and including 30 days after the end of blinatumomab or pembrolizumab whichever is later.**

Subject incidence of all, serious, grade 3 and above, leading to withdrawal of investigational product, leading to interruption of investigational product, fatal, treatment-related, **treatment-related serious, and treatment-related grade 3 and above** treatment-emergent adverse events (**including DREs**) will be tabulated by system organ class and preferred term in descending order of frequency **for highest dose group**.

Treatment-emergent events of interest (EOIs) will be summarized by EOI category and preferred term. In addition, for each EOI category, the subject incidence of all, serious, **grade 3 and above, grade 4 and above**, fatal, leading to withdrawal of investigational product, leading to interruption of investigational product will be summarized. **Time to onset, duration, number of selected EOIs will also be summarized.**

Additionally, treatment emergent DREs and fatal DREs will be summarized by system organ class and preferred term in descending order of frequency **for highest dose group**. Subject incidence of ECIs will be summarized by ECI category and preferred term in descending order of frequency **for highest dose group**.

Subgroup analyses of treatment-emergent adverse events will be presented for age-group (< 65, 65-74, ≥ 75), and gender by system organ class and preferred term in descending order of frequency for highest dose group.

Subject listings of Serious AEs, Fatal AEs and Deaths will be provided. Analyses will be performed based on Safety Analysis Set.

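### Serious adverse events and serious disease-related events are collected to 90 days after treatment but tabulated only to 30, and the SAP does not declare the cut-off

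*SAP*

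**What the plan says.** **SAP.** Section 6.1 counts an adverse event as treatment-emergent if it starts between the first blinatumomab dose and 30 days after the later last dose, and adds: "This reporting window also applies to treatment-emergent serious adverse events (SAEs". It defines a treatment-emergent DRE in the same way: "a disease-related event that starts on or after first dose of blinatumomab up to and including 30 days after the end". Section 10.6.2 repeats the window ("up to and including 30 days after the end of blinatumomab or pembrolizumab whichever is later") and builds on it the incidence tables for all, serious, grade 3 or higher, fatal and treatment-related events, with DREs included. The event-of-interest tables are also restricted to treatment-emergent events. Separately, "treatment emergent DREs and fatal DREs will be summarized by system organ class and preferred term". The individual-level output is: "Subject listings of Serious AEs, Fatal AEs and Deaths will be provided". Section 11 declares changes only to the timing of the primary analysis and to the DOR and PFS definitions.

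**Protocol.** SAEs are collected from consent through "90 days following cessation of treatment, or 30 days following cessation of treatment if the subject initiates new anticancer therapy", whichever is earlier (9.2.2.2). Section 9.1.3 gives the same period: "for the time period beginning with signing of informed consent through 90 days following cessation of treatment". Serious DREs have the same end point and "are recorded on the Event CRF as a serious Disease Related Event" (9.2.1.2). Section 7.2.3 adds a 7-day allowance to both the 90-day and the 30-day limit for SAEs. Section 10.4.2.3 defines treatment-emergent events by onset after the first dose, with no end, and includes DREs in those analyses.

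**The concern.** The study's hypothesis is that the combination is tolerable, and the incidence and severity of adverse events is its safety endpoint. Protocol 6.2.2.2.2 warns that immune-related events can appear months after the last pembrolizumab dose, which is a reason to follow serious events to 90 days. If the tables stop at 30 days, serious toxicity that sites were required to report can be absent from every incidence figure. Some serious DREs may not appear in the report at all. A reader who compares the SAP with the protocol would not learn of the narrowing from SAP 11.

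Cohorts are small, with 6 subjects or 10 if expanded. One additional subject with a late serious event would add 1/6 = 17 or 1/10 = 10 percentage points to that cohort's incidence.

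**Working it through.** The check sets the two windows side by side and subtracts. The common anchor is the end of all study treatment: the SAP uses the later last dose, and protocol 7.2.3 uses cessation of all study treatment.

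| Event type | Protocol collection after last dose | SAP tables | Days collected but not tabulated |
|---|---|---|---|
| SAEs and serious DREs, no new therapy | 90 days (9.2.2.2, 9.2.1.2) | 30 days | 90 − 30 = 60 |
| SAEs, no new therapy, with the 7.2.3 allowance | 97 days | 30 days | 97 − 30 = 67 |
| SAEs and serious DREs, collection cut to 30 days by new therapy | 30 days | 30 days | 0 |
| SAEs, same case, with the 7.2.3 allowance | 37 days | 30 days | 37 − 30 = 7 |
| Non-serious AEs and DREs (9.2.2.1, 9.2.1.1) | visit at 30 (+7) days | 30 days | 0 to 7 |
| Events of clinical interest (9.1.4) | 30 days | 30 days | 0 |

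As a share of post-treatment collection, 60/90 = 67%, or 67/97 = 69% with the allowance.

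**A full-length example.** Table 7-2 places cycle 35 of pembrolizumab on day 729 for cohort Ia. The tables then stop at 729 + 30 = day 759, which matches the safety visit in that table, and collection runs to 729 + 90 = day 819. For cohorts IIa and IIIa (Table 7-4, cycle 35 on day 733) the corresponding days are 763 and 823.

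**Where a serious event with onset on days 31 to 90 goes:**

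1. *An SAE.* It is not treatment-emergent under SAP 6.1, so it enters no incidence table. It does appear in the SAE listing, because that listing is not limited to treatment-emergent events.
2. *A serious DRE judged related or worse than expected.* Protocol 9.2.1.2 and SAP 6.1 require it to be recorded as an SAE, so it follows route 1.
3. *Any other non-fatal serious DRE.* It is outside the treatment-emergent DRE table. The listing sentence names serious AEs, fatal AEs and deaths, and protocol 9.1.1 says a DRE is not an adverse event unless upgraded. Read literally, no planned output contains it.
4. *A fatal DRE.* The death is listed. Whether the event enters the fatal-DRE summary is unclear, because the SAP does not say whether the 30-day limit governs that summary.

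**Declaration.** Protocol 10.4.2.3 sets a start and no end for treatment emergence, and asks for fatal adverse events to be tabulated without restricting them to treatment-emergent ones. The SAP restricts both, and SAP 11 mentions neither.

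**The case against.** A collection window and a treatment-emergent window need not coincide. A 30-day analysis window is a normal choice, and supplying an end date that the protocol leaves open is part of what a SAP is for. This stands, and it is why the 30-day tables should stay. It does not explain why the cut-off is undeclared, or why part of the collected serious data has no summary.

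Late SAEs are in the listing, and with at most 30 subjects a reader can count them. That is true, but a listing gives no incidence by cohort or preferred term, and as worded it does not cover serious DREs.

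The DREs left out are non-fatal, expected in severity and judged unrelated, and PFS captures radiographic progression. This limits the consequence: the warning about late immune-related events bears mainly on SAEs. It does not put those DREs into an output. One could read the listing as meant to include serious DREs, but the SAP adds the words about DREs only to the incidence tables, and protocol 9.1.1 separates the two categories.

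The 67% is a share of post-treatment days only. Over all of a cohort Ia subject's follow-up through 35 cycles it is 60/819 = 7%. Both figures are correct for their denominators. The share of total follow-up is larger for subjects who stop early.

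The SAP was written for protocol amendment 5 and the protocol supplied is amendment 6, whose stated purposes include safety reporting. In 7.2.3, 9.1.3, 9.2.1.2 and 9.2.2.2 the 90-day text is not in the bold used for added wording, and the amendment 4 summary already mentions revised language for serious DREs and SAEs. This suggests the text is older but does not prove it. For DREs the evidence is weak, because the same footnote is bold in Table 7-3 and plain in Table 7-1.

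**Conclusion.** The concern holds. For subjects who start no new anticancer therapy, up to 60 of 90 post-treatment collection days for serious events (67%; 67 of 97, or 69%, with the 7.2.3 allowance) are outside every incidence table. SAEs in that period are listed only. Non-fatal serious DREs not reclassified as SAEs are in no planned output on the literal wording, and the cut-off is not recorded in SAP 11. Where new therapy has cut collection to 30 days, the gap is 0 to 7 days. For non-serious events and events of clinical interest the SAP window fits, apart from at most 7 days.

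These are days, not events; no post-treatment rate is given, so the number of events cannot be estimated. With Part 2 dropped, at most 30 subjects are concerned. The DLT and MTD assessment is essentially unaffected, since it uses its own 42-day window from first pembrolizumab, and OS counts all deaths. The change should be made, but the primary result does not depend on it. The conclusion assumes that the 90-day rule already applied under amendment 5.

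**What to change.** Keep the 30-day treatment-emergent tables and make these changes to the SAP:

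- **10.6.2, one supplementary incidence table.** SAEs (all, treatment-related, fatal) and serious DREs, with onset from the first blinatumomab dose through 90 days after the last dose of either drug, or 30 days if new anticancer therapy starts earlier.
- **10.6.2, listings.** Add serious DREs to the subject listings.
- **10.6.2, later reports.** List related or fatal SAEs reported after that window separately and leave them out of any incidence, because protocol 9.2.2.3 no longer requires monitoring by then.
- **10.6.2, fatal DREs.** State which window the fatal-DRE summary uses.
- **11.** Record the 30-day end of treatment emergence as a change from protocol 10.4.2.3.

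The cost is SAP wording, one table and one listing, from data already on the Event CRF. The one drawback is a second SAE count, which needs a footnote explaining the two windows.

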6.2 Efficacy Endpoints

Complete Response (CR) Rate by the Lugano Classification

Complete **response rate by the Lugano Classification** is the proportion of subjects who have achieved complete **response by the Lugano Classification (Cheson et al, 2014) during the first 12 weeks** since starting blinatumomab **and during the treatment period** among all subjects in the respective analysis set.

Complete Response (CR) Rate by the Revised Response Criteria

Complete **response rate by the Revised Response Criteria** is the proportion of subjects who have achieved complete **response by the Revised Response Criteria (Cheson et al, 2007) during the first 12 weeks** since starting blinatumomab **and during the treatment period** among all subjects in the respective analysis set.

Duration of Response (DOR) by Lugano Classification

Duration of response will be calculated only for subjects who achieve an OR (ie, CR or PR) by **Lugano Classification (Cheson et al, 2014)** criteria **during the first 12 weeks since** starting blinatumomab. The duration will be calculated from the date a response, CR or PR, is first achieved until the earliest date of a disease assessment indicating a disease progression or death, whichever occurs first. **For diagnosis of progression of lymphoma, the progression of radiographic assessment of PET-CT using Lugano Classification will be used.** Subjects who do not have a relapse event will be censored on their last radiological non-missing evaluable tumor assessment date.

Duration of Response (DOR) by Revised Response Criteria (Cheson et al, 2007)

Duration of response will be calculated only for subjects who achieve an OR (ie, CR or PR) by **Revised Response Criteria (Cheson et al, 2007)** criteria during the first 12 weeks since starting blinatumomab. The duration will be calculated from the date a response, CR or PR, is first achieved until the earliest date of a disease assessment indicating a disease progression or death, whichever occurs first. **For diagnosis of progression of lymphoma, the progression of radiographic assessment of PET-CT using Revised Response Criteria (Cheson et al, 2007) will be used.** Subjects who do not have a relapse event will be censored on their last radiological non-missing evaluable tumor assessment date.

Objective Response by the Lugano Classification

Objective response (including CR and PR) by the Lugano Classification is determined by the Lugano Classification (Cheson et al, 2014) during the first 12 weeks since starting blinatumomab and during the treatment period.

Objective Response by the Revised Response Criteria

Objective response (including CR and PR) by the Revised Response Criteria is determined by the Revised Response Criteria (Cheson et al, 2007) during the first 12 weeks since starting blinatumomab and during the treatment period.

Objective Response Rate (ORR) by the Lugano Classification

Objective response rate (ORR) **by the Lugano Classification** is the proportion of subjects who have achieved either a CR or a PR among subjects by **the Lugano Classification (Cheson et al, 2014)** during the first 12 weeks since starting blinatumomab **and during the treatment period** in the respective analysis set.

Objective Response Rate (ORR) by the Revised Response Criteria

Objective response rate (ORR) **by the Revised Response Criteria** is the proportion of subjects who have achieved either a CR or a PR among subjects by **the Revised Response Criteria (Cheson et al, 2007)** during the first 12 weeks since starting blinatumomab **and during the treatment period** in the respective analysis set.

Overall Survival (OS)

The overall survival will be calculated as the time from the date of first dose of blinatumomab until death due to any cause. Subjects who are alive at the date that triggers the analysis will be censored at the date last known to be alive.

Progression Free Survival (PFS) by Lugano Classification

The PFS will be calculated as the time from the date of first dose of blinatumomab until the date of diagnosis of progression of lymphoma, or date of death, whichever is earliest. **For diagnosis of progression of lymphoma, the progression of radiographic assessment of PET-CT using Lugano Classification will be used.** Subjects who are alive and did not have progression will be censored at the last **radiological non-missing evaluable** tumor assessment date.

Progression Free Survival (PFS) by Revised Response Criteria

The PFS will be calculated as the time from the date of first dose of blinatumomab until the date of diagnosis of progression of lymphoma, or date of death, whichever is earliest. **For diagnosis of progression of lymphoma, the progression of radiographic assessment of PET-CT using Revised Response Criteria will be used.** Subjects who are alive and did not have progression will be censored at the last radiological non-missing evaluable tumor assessment date.

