8.4 Lost to Follow-up

A subject will be considered lost to follow-up if he or she repeatedly fails to return for scheduled visits and is unable to be contacted by the study site.

The following actions must be taken if a subject fails to return to the clinic for a required study visit:

- The site must attempt to contact the subject and reschedule the missed visit as soon as possible and counsel the subject on the importance of maintaining the assigned visit schedule and ascertain whether or not the subject wishes to and/or is able to continue in the study.
- In cases in which the subject is deemed lost to follow-up, the investigator or designee must make every effort to regain contact with the subject (where possible, 3 telephone calls and, if necessary, a certified letter to the subject's last known mailing address or local equivalent methods). These contact attempts are to be documented in the subject's medical record.
- If the subject continues to be unreachable, he/she will be considered to have withdrawn from the study with a primary reason of lost to follow-up.
- For subjects who are lost to follow-up, the investigator can search publicly available records where permitted to ascertain survival status. This ensures that the data set(s) produced as an outcome of the study is/are as comprehensive as possible.

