10.1.1.2 Secondary Endpoints

- Objective response (including CR and PR) by the Lugano Classification (Cheson et al, 2014) and Revised Response Criteria (Cheson et al, 2007) during the first 12 weeks since starting blinatumomab and during the treatment period
- Complete response by the Lugano Classification (Cheson et al, 2014) and Revised Response Criteria (Cheson et al, 2007) during the first 12 weeks since starting blinatumomab and during the treatment period
- Progression free survival: will be calculated as the time from the date of first dose of blinatumomab until the date of diagnosis of progression of lymphoma, or date of death, whichever is earliest. For diagnosis of progression of lymphoma, the progression of radiographic assessment of PET/CT using Lugano Classification will be used. Subjects who are alive and did not have progression will be censored at the last radiological non-missing evaluable tumor assessment date. Progression free survival for subjects who were enrolled in dose cohorts that were not selected for the extension cohort will not be calculated.
- Overall survival: will be calculated as the time from the date of first dose of blinatumomab until death due to any cause. Subjects who are alive at the date that triggers the analysis will be censored at the date last known to be alive.
- Duration of response: calculated only for subjects who achieve an OR (ie, CR or PR) during the first 12 weeks since starting blinatumomab. The duration will be calculated from the date a response, CR or PR, is first achieved until the earliest date of a disease assessment indicating a relapse event or death, whichever occurs first. For diagnosis of progression of lymphoma, the progression of radiographic assessment of PET/CT using Lugano Classification will be used. Subjects who do not have a relapse event will be censored on their last radiological non-missing evaluable tumor assessment date. A sensitivity analysis will censor subjects who receive an autologous HSCT/allogenic HSCT at the time of autologous HSCT/allogenic HSCT unless there is no assessment after the autologous HSCT/allogenic HSCT, in which case the last assessment prior to the autologous HSCT/allogenic HSCT will be used as the censoring time.
- Blinatumomab PK parameters
- Pembrolizumab PK parameters

Note that “remission” in this context equates to “response.”

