Handling Incomplete Dates and Missing Dates for Adverse Events and Concomitant Medications.

The following data will be imputed using the following algorithm:

- Adverse Events
- Concomitant Medications

Imputation Rules for Partial or Missing Start Dates

Start Date		Stop Date						Missing
		Complete: yyyymmdd		Partial: yyyymm		Partial: yyyy		
		< 1 st dose	≥ 1 st dose	< 1 st dose yyyymm	≥ 1 st dose yyyymm	< 1 st dose yyyy	≥ 1 st dose yyyy	
Partial: yyyymm	= 1 st dose yyyymm	2	1	2	1	n/a	1	1
	≠ 1 st dose yyyymm		2		2	2	2	2
Partial: yyyy	= 1 st dose yyyy	3	1	3	1	n/a	1	1
	≠ 1 st dose yyyy		3		3	3	3	3
Missing		4	1	4	1	4	1	1

1 = Impute the date of first dose
 2 = Impute the first of the month
 3 = Impute January 1 of the year
 4 = Impute January 1 of the stop year

Note: If the start date imputation leads to a start date that is after the stop date, then do not impute the start date.

Imputation rules for partial or missing stop dates:

Initial imputation

- For partial stop date mmyyyy, impute the last of the month.
- For partial stop date yyyy, impute December 31 of the year.
- For completely missing stop date, do not impute.

- If the stop date imputation leads to a stop date that is after the death date, then impute the stop date as the death date.
- If the stop date imputation leads to a stop date that is before the start date, then there is a data error and do not impute the stop date. (ie. set the stop date as missing).

Imputation rules for partial or missing death dates:

- If death year and month are available but day is missing:
- If mmyyyy for last contact date = mmyyyy for death date, set death date to the day after the last contact date.
- If mmyyyy for last contact date < mmyyyy for death date, set death date to the first day of the death month.
- If mmyyyy for last contact date > mmyyyy for death date, data error and do not impute.

If both month and day are missing for death date or a death date is totally missing, do not impute.

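### Duration of response counts death as an event, but its censoring sentence has no alive condition and, read literally, censors a responder who dies in remission

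*SAP*

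**What the plan says.** **DOR.** SAP 6.2 runs DOR from first response "until the earliest date of a disease assessment indicating a disease progression or death, whichever occurs first", once for the Lugano Classification and once for the Revised Response Criteria. Protocol 10.1.1.2 has "until the earliest date of a disease assessment indicating a relapse event or death, whichever occurs first". Each definition is followed by the same censoring sentence: "Subjects who do not have a relapse event will be censored on their last radiological non-missing evaluable tumor assessment date". Neither document defines a relapse event.

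**PFS and OS.** SAP 6.2 limits PFS censoring to the living: "Subjects who are alive and did not have progression will be censored at the last radiological non-missing evaluable tumor assessment date". OS is limited in the same way: "Subjects who are alive at the date that triggers the analysis will be censored at the date last known to be alive".

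**Death dates.** SAP Appendix A imputes a missing day when month and year are known. Beyond that: "If both month and day are missing for death date or a death date is totally missing, do not impute". A death month that precedes the last-contact month is also left alone: "If mmyyyy for last contact date > mmyyyy for death date, data error and do not impute". SAP 9.3 analyses only non-missing data, apart from counting subjects without a tumor assessment as non-responders. SAP 6.1 takes death dates from several CRF pages. Under protocol 8.4, for subjects lost to follow-up, "the investigator can search publicly available records where permitted to ascertain survival status".

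SAP Section 11 revises the DOR and PFS definitions and records that Part 2 will not open. It settles neither point.

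**The concern.** A responder who dies in remission meets the DOR event definition and also the censoring condition. The two give different data records: an event at the death date, or a censored time at the last scan. Two programmers could follow the SAP faithfully and report different DOR curves.

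Censoring at death is informative, because the subject has failed under the endpoint's own definition. Two features of this study add to the problem:

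- Protocol 7.3.12.3 continues scheduled PET/CT only until complete remission, progression or relapse, or 24 months. For a complete responder the last scan may be the one that documented the remission, so the censored time can be close to zero.
- With Part 2 dropped, DOR rests on Part 1 responders. SAP 10.1 analyses Part 1 by cohort, and a cohort has at most 10 subjects.

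Separately, a subject known to be dead but without a usable date has no stated place in the OS and PFS analyses, although SAP 10.5 runs both on the full analysis set.

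**Working it through.** The plan gives no event count, median or power for DOR, OS or PFS, so there is no figure to reproduce. The check is textual, with arithmetic to show size.

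**1. The censoring rules side by side**

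| Endpoint | Event | Who is censored | Alive required? |
|---|---|---|---|
| OS (SAP 6.2) | death | the living | yes |
| PFS (SAP 6.2) | progression or death | living, no progression | yes |
| DOR (SAP 6.2, both criteria) | progression or death | no relapse event | no |
| DOR (protocol 10.1.1.2) | relapse event or death | no relapse event | no |

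The protocol lists relapse event and death as alternatives, so there a relapse event does not include death. The SAP changes the event term to progression but keeps the older term in the censoring sentence.

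**2. One death among 4 responders**

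Four is an assumption. It is close to what a cohort of 10 gives at the 42.9% monotherapy ORR cited in protocol 2.1: 10 × 0.429 = 4.3. With the death in remission as the first event:

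- counted as an event: 1 − 1/4 = 0.75
- censored: 1.00

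**3. Ten hypothetical responders**

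Times are 2, 3, 4, 5, 6, 8, 9, 11, 14 and 18 months. The first eight are events, and those at 3, 6 and 9 are deaths without relapse.

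- Deaths as events: S(6) = 5/10 = 0.50; median 6 months.
- Deaths censored at the last scan: the death at 3 moves to 0.1 (a complete responder with no later scan), and those at 6 and 9 move to 5.5 and 8.3. Then S(6) = 8/9 × 7/8 × 6/7 = 0.67. At 8 months S = 0.67 × 4/5 = 0.53, and at 11 months 0.53 × 2/3 = 0.36. The median is 11 months.

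**4. Large-sample size**

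The share q of DOR events that are deaths without relapse is an assumption, with range 10% to 40%. For exponential times, censoring at death multiplies the median by 1/(1 − q). A simulation (20,000 responders, true median 6 months, scans every 12 weeks, 24 months) gives the 12-month DOR probability:

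| q | 1/(1 − q) | Deaths as events | Censored at last scan | As previous, but half are complete responders censored at time 0 if they die |
|---|---|---|---|---|
| 10% | 1.11 | 0.28 | 0.32 | 0.30 |
| 20% | 1.25 | 0.27 | 0.36 | 0.33 |
| 30% | 1.43 | 0.27 | 0.41 | 0.36 |
| 40% | 1.67 | 0.26 | 0.46 | 0.39 |

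The direction is upward throughout. Stopping scans at complete remission discards follow-up time, but in this model it does not enlarge the bias, because those subjects also leave the early risk sets.

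**5. Known deaths without a usable date**

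Appendix A supplies no event date, and the OS and PFS censoring rules exclude the dead. Neither time exists. If a programmer censors the first of 6 deaths, the gap is 1 − 5/6 = 17 points at that death and 4/5 − 4/6 = 13 points at the next. If all 6 die and the last death is dropped, survival after the fifth is 0 instead of 1/6, so the curve falls.

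In a simulation with true median OS of 12 months and undated deaths arising at random, the median is about 12.1 with all deaths dated. With 10% undated it is 12.9 if they are dropped and 13.4 if they are censored. With 3% to 5% undated the shift is about 0.2 to 0.5 month. These shares are assumptions.

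**The case against.** The best defence on DOR is that the definition plainly counts death, and a censoring rule ordinarily applies only to subjects without an event. In the SAP, relapse event can be read as shorthand for any DOR event. That is a fair reading and may be the intended one. It also means that a reader should not infer that the sponsor chose to censor deaths in remission: this is inconsistent wording. But the defence does not remove the ambiguity. The protocol separates relapse from death, and the PFS rule in the same SAP section shows the clear form.

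A reader might also infer that the plan censors known deaths in OS and PFS and so biases all three endpoints upward. The documents do not support that. Both censoring rules are confined to living subjects, so the fault is a missing rule. Upward bias is likely on average, but step 5 shows that dropping a late death can lower a small-sample curve. The 17-point gap there is a maximum, reached at the death itself.

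Undated deaths should also be uncommon. Several CRF pages collect the date, fatal events are reported within 24 hours of awareness (protocol 9.2.1.2 and 9.2.2.3), survival contact is every 12 weeks, and SAP 9.1 sends open data issues for resolution before lock. Not imputing a fully missing date is a defensible choice for the main analysis. All of this stands, and it makes the death-date gap secondary.

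**Conclusion.** The DOR conflict is in the text of both documents and should be corrected. If the literal censoring sentence is programmed, DOR is overstated whenever a responder dies without relapse: 75% against 100% for one first death among 4 responders, and a median multiplied by 1.11 to 1.67 if 10% to 40% of DOR events are such deaths. The number of responders and the share of deaths are assumptions; the documents give neither.

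The handling of known deaths without a usable date is a genuine gap but a minor one, of uncertain direction and probably small. For PFS it matters only when there was no earlier documented progression.

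These are descriptive secondary endpoints. DLT incidence, ORR and the stopping rules do not depend on either point.

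**What to change.** **DOR.** In SAP 6.2 (both criteria), replace the censoring sentence with wording to this effect, and align protocol 10.1.1.2 if it is amended again: *Responders who are alive without progression or relapse are censored at their last evaluable radiological tumor assessment; death without earlier progression or relapse is an event.* This matches the PFS rule and costs one sentence.

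**Undated deaths.** Report the number of known deaths without a usable date and state how the main OS and PFS analyses treat them. Add a flagged sensitivity analysis that counts them as events on the day after last contact or, for year-only dates, on the later of that day and 1 January of the death year. Say openly that the imputed date may be materially early: by up to nearly 12 months for a year-only date, and without a known bound for a fully missing one. That is why it belongs in a sensitivity analysis. The cost is a short addition to Appendix A and one extra run, needed only if such deaths occur.
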